## NON-INTERVENTIONAL (NI) STUDY PROTOCOL

### PASS Information

Title	An Active Surveillance, Post-Authorization Safety Study (PASS) to Estimate Incidence Rates of Serious Infection, Malignancy, Cardiovascular (CV) and Other Safety Events of Interest Among all Patients Treated with Ruxience for Rheumatoid Arthritis (RA) Within the Swedish, Population-based, Anti-Rheumatic Treatment in Sweden (ARTIS) Register
Protocol number	B3281013
Protocol version identifier	1
Date	14 October 2020
EU Post Authorisation Study (PAS) register number	To be determined
Active substance	PF-05280586 Rituximab
Medicinal product	Ruxience (rituximab)
Product reference	H0004696
Procedure number	EMA/H/C/004696/0000
Marketing Authorisation Holder (MAH)	Pfizer Europe MA EEIG
Joint PASS	No
Research question and objectives	Research Question: What are the incidence rates of safety events of special interest in patients with rheumatoid arthritis in the ARTIS register who are treated with

090177e1953e1418\Approved\Approved On: 16-Oct-2020 13:21 (GMT)

PFIZER CONFIDENTIAL

CT24-WI-GL02-RF02 2.0 Non-Interventional Study Protocol Template For Secondary Data Collection Study

01-Jun-2020

Page 1

	Ruxience?  Objectives: To estimate incidence rates of infections, including serious infections, malignancies, cardiovascular events, and use during pregnancy among patients with rheumatoid arthritis in the ARTIS register who initiate Ruxience.
Country(-ies) of study	Sweden
Author	[name], PhD, MPH Safety Surveillance Research, Worldwide Medical and Safety, Pfizer, Inc. [name]

Marketing Authorisation Holder(s)	Pfizer Europe MA EEIG [name]
MAH contact person	[name], PhD, MPH [name]

This document contains confidential information belonging to Pfizer. Except as otherwise agreed to in writing, by accepting or reviewing this document, you agree to hold this information in confidence and not copy or disclose it to others (except where required by applicable law) or use it for unauthorized purposes. In the event of any actual or suspected breach of this obligation, Pfizer must be promptly notified.

090177e1953e1418\Approved\Approved On: 16-Oct-2020 13:21 (GMT)

## 2. LIST OF ABBREVIATIONS

Abbreviation	Definition
ACR	American College of Rheumatology
ACS	acute coronary syndrome
ADR	adverse drug reaction
AE	adverse event
ARTIS	Anti-Rheumatic Treatment in Sweden
AS	ankylosing spondylitis
CLL	Chronic lymphocytic leukemia
CRP	C-reactive protein
CV	cardiovascular
CVD	cardiovascular disease
DALYS	Daily-adjusted Life Years
DAS-28	Disease Activity Score in 28 joints
DMARD	Disease modifying anti-rheumatic drug
EEIG	European Economic Interest Grouping
EMA	European Medicines Agency
ENCEPP	European Network of Centres for Pharmacoepidemiology and Pharmacovigilance
ESR	erythrocyte sedimentation rate
EU	European Union
GEP	Good Epidemiological Practice
GPA	Granulomatosis with polyangiitis
GVP	Good pharmacovigilance practices
HAQ	health Assessment Questionnaire
HRQoL	Health-related Quality of Life
ICD	International Classification of Diseases
IEC	Independent Ethics Committee
IRB	Institutional Review Board
IT	Information Technology
MA	Market Authorisation
MACE	Major acute cardiovascular event
MAH	Market Authorisation Holder
MedDRA	Medical Dictionary for Regulatory Activities
MI	myocardial infarction
MPA	Microscopic polyangiitis
N	number
N/A	Not applicable
NHL	Non-Hodgkin's lymphoma
NI	Non-interventional
NMSC	non-melanoma skin cancer

Abbreviation	Definition
NNH	number needed to harm
NSAIDs	nonsteroidal anti-inflammatory drugs
PASS	Post-Authorization Safety Study
PPV	positive predictive value
PsA	psoriatic arthritis
PV	Pemphigus Vulgaris
QALY	Quality-adjusted Life Year
RA	rheumatoid arthritis
RMP	Risk Management Plan
SAP	Statistical Analysis Plan
SRQ	Swedish Rheumatology Quality Register
TNF	Tumor necrosis factor
VAS	visual analog scale

090177e1953e1418\Approved\Approved On: 16-Oct-2020 13:21 (GMT)

#### 4. ABSTRACT

**Title:** An Active Surveillance, Post-Authorization Safety Study (PASS) to Estimate Incidence Rates of Serious Infection, Malignancy, Cardiovascular (CV) and Other Safety Events of Interest Among all Patients Treated with Ruxience for Rheumatoid Arthritis (RA) Within the Swedish, Population-based, Anti-Rheumatic Treatment in Sweden (ARTIS) Register.

**Version:** 1

**Date:** 14 October 2020

**Main Author:** [name], Pfizer, Inc.

#### **Rationale and background:**

Rituximab is a genetically engineered chimeric mouse/human monoclonal IgG1k antibody targeting the transmembrane CD20 antigen. CD20 is a 32-kDa, non-glycosylated transmembrane phosphoprotein, located on the surface of normal precursor-B cells, mature B lymphocytes and malignant B cells. The natural ligand for CD20 has not been identified, and the biological function of CD20 remains unclear. Rituximab binds to a discontinuous conformational epitope on CD20 and initiates multiple immune effector functions leading to target cell lysis. The currently approved indications for licensed rituximab (MabThera) are for Rheumatoid arthritis (RA), Non-Hodgkin's lymphoma (NHL), Chronic lymphocytic leukaemia (CLL), Granulomatosis with polyangiitis (GPA), Microscopic polyangiitis (MPA) and Pemphigus vulgaris (PV).

Licensed as MabThera in the European Union (EU) in 1998, rituximab was the first biologic on the market for RA for specific B cell targeting therapy. Rituximab in combination with methotrexate is indicated for the treatment of adult patients with severe active RA who have had an inadequate response or intolerance to other disease-modifying antirheumatic drugs (DMARDs) including one or more tumour necrosis factor (TNF) inhibitor therapies. Approved in the EU on 01 April 2020, PF-05280586 (Ruxience) has been developed by Pfizer as a biosimilar to the licensed reference product, MabThera. Pfizer proposes the assessment of safety events of special interest based on the Ruxience EU Risk Management Plan (RMP) version 1.0 (infections including serious infections (Important Identified Risk), malignancies (Important Potential Risk), impact on cardiovascular disease (CVD) (Important Potential Risk) and use in pregnancy (Missing Information)). This protocol describes a non-interventional, Post-Authorisation Safety Study (PASS) of Ruxience-exposed patients using actively collected prospective data included in the established Anti-Rheumatic Therapies in Sweden (ARTIS) register.

**Research question:** What are the incidence rates of safety events of special interest in patients with RA who initiate Ruxience in the ARTIS register?

**Objectives:** To estimate incidence rates of infections, including serious infections, malignancies, cardiovascular events, and use during pregnancy among all patients with rheumatoid arthritis in the ARTIS register who initiate Ruxience.

**Study design:** This active surveillance study uses data from the established ARTIS register, an ongoing, prospective, disease-based cohort started in 1999 with the primary aim of evaluating the safety of RA patients who are started on new biologic therapies for RA during routine post-marketed clinical use. This study is a secondary data collection study of anonymised, structured data in ARTIS.

**Population:** The study population will comprise of all patients with RA enrolled within the ARTIS register who initiate treatment with Ruxience.

**Data sources:** The Swedish Rheumatology Quality Register (SRQ) was started in 1995 by the Swedish Society of Rheumatology to improve the healthcare and treatment for patients with RA. SRQ followed on regional register initiatives, to enable a national real world documentation of many different aspects of RA and developed over time into a harmonised national register. SRQ was started mainly for patients with RA, but over time it has been expanded to cover several other rheumatic diseases. Initially focusing on early RA, SRQ has gradually come to include other segments. Data entry into SRQ is provided by the patient and the rheumatologist in conjunction with visits. Visits are scheduled according to treatment guidelines and clinical practice, at 0 and 3 to 6 months after the initiation of a new anti-rheumatic therapy, and thereafter in relation to the level of disease activity, according to an overall treat to target paradigm. Data are routinely captured as patients must visit their physician annually to renew prescriptions and must refill prescriptions every three months.

Mandated by the Swedish Society of Rheumatology, ARTIS is a research project hosted by the Karolinska Institutet. Since 1999, ARTIS has conducted a safety surveillance programme for immunomodulators based on SRQ linked to additional registers and includes all presently available biologics used for the treatment of patients with inflammatory rheumatic diseases. It covers around 90% of all biologic initiations in Sweden after 1999.

**Variables:** This study will use data routinely captured in the ARTIS register, which include baseline patient characteristics (ie, demographic and clinical characteristics, comorbidities and current and past therapies), and safety events of special interest including serious infections, all malignancies, CVD events, and use during pregnancy. Infectious and cardiovascular events will be ascertained through record linkage with the Swedish Patient Register, which collects information on all hospitalised patients, and all visits to non-primary outpatient care. Diagnoses are assigned by the discharging/treating physician, as well as date of discharge/visit, hospital and department. Malignancies will be ascertained through linkage with the Swedish Cancer Register which contains data on date of cancer diagnosis and type of cancer according to the International Classification of Disease (ICD). Use in pregnancy will be assessed through additional linkage with the Medical Birth Register which contains data from antenatal, obstetric, and neonatal records, and covers all live and still births (but not all miscarriages) in Sweden.

**Study size:** This is a descriptive study. All Ruxience-treated patients in the ARTIS register during the study period will be included in the study.

**Study period:** The Study Start Date is defined as the date when the first patient diagnosed with RA in ARTIS initiates treatment with Ruxience. The Study End Date is defined as 3 years after the Study Start Date.

**Data analysis:** Annual reports will contain information on uptake of Ruxience and patient characteristics. Interim and final study reports will consist of descriptive summaries of baseline variables and incidence rates based on data linkage for safety events of interest described above for Ruxience-treated patients. No comparative analyses with other cohorts will be performed.

**Milestones:** The first annual report describing the number and characteristics of patients initiating Ruxience is expected by 15 July 2021 and annually thereafter through 15 July 2023. An interim report and a final report containing incidence rates of events of special interest will be prepared by 01 July 2023 and 31 December 2024, respectively.

## 5. AMENDMENTS AND UPDATES

None.

090177e1953e1418\Approved\Approved On: 16-Oct-2020 13:21 (GMT)

## 6. MILESTONES

Milestone	Planned date
Registration in the EU PAS register	TBD
Start of data collection (estimated)	01 July 2021 ^
Date of first annual report (estimated)	15 July 2021
Date of second annual report (estimated)	15 July 2022
Date of interim report	01 July 2023
Date of third annual report (estimated)	15 July 2023
End of data collection (estimated)	31 December 2023 #
Final study report (estimated)	31 December 2024 x

^ Start of data collection is the planned date for starting data extraction for the purposes of the study analysis.

# End of data collection is the planned date on which the analytical dataset will be first completely available; the analytic dataset is the minimum set of data required to perform the statistical analysis for the study objective(s).

x Final report must be prepared within 11 months of end of data collection.

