#### 9.3.2. Follow-Up and Risk Window

Patients will be followed from treatment start (Index Date) until each outcome of interest, death, emigration from Sweden and end of study follow-up treated as censoring events. The Study End Date is defined as 3 years after the Study Start Date (date when first patient diagnosed with RA in ARTIS initiates treatment with Ruxience).

Some outcomes of interest in this study are thought to potentially occur at a higher rate while on drug, but that increased risk subsides after the drug is discontinued (ie, serious infections, CV events). Those events will be evaluated over a risk window that includes time from drug initiation until 270 days (eg, 9 months) after end of treatment (ie, last dose of Ruxience). The 270-day extension period is implemented to accommodate the very long half-life of Ruxience, and to ensure that any subclinical or undiagnosed illness at time of end of treatment is captured. For non-melanoma skin cancer (NMSC) and other malignancies, the manifestation of which is expected to be delayed relative to the time of exposure, the outcomes will be evaluated from drug initiation until the first event or loss to follow up, reflecting a once-exposed always at-risk paradigm.

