### 9.4.2. SRQ/ARTIS Linkage

Endpoint information will be derived from the linkage of SRQ/ARTIS to nationwide Swedish health care registers. The register linkage has many advantages in providing data on all comorbidities that have been diagnosed. The drawback is a lag time of between 1 and 2 years from when an event occurs until it can be analysed and reported using the national health care registers. This delay is caused by the annual curation of the Patient and Cancer registers by the National Board of Health and Welfare (ie, data from each year is only made available after internal processing, usually 9 to 12 months later, and the processing of data requests.

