## 9.9. Limitations of the Research Methods

This study is designed to monitor the safety of Ruxience in the clinical practice setting utilising the ARTIS Register, a well-established Swedish-based rheumatology register. Despite the strengths of the register, data must be evaluated in light of their limitations. For example, consistent with most observational studies, the possibility of endpoint misclassification, is of concern in interpreting findings.

As a new therapy in the RA treatment armamentarium, it is possible that patients treated with Ruxience will represent those with the most severe cases of disease, longer disease duration, history of multiple failed RA therapies and physical comorbidities that place patients at risk for events. Biases resulting from channeling may present as increased rates of safety events of interest in the early phases of the study. Stratification on key indicators of disease severity, patient characteristics and past therapies can be done for contextualisation. Trend analyses may be conducted to evaluate rates in Ruxience patients over time.

The RA treatment landscape has evolved over time with the introduction of new therapies, treatment recommendations, and approaches to patient management. The rates of safety events of interest and their distribution among patient-types may have changed over time.

Endpoint misclassification is of particular concern within the observational setting due to less stringent monitoring relative to clinical trials. While ARTIS has an established system to identify and capture endpoint data, all events cannot be fully verified via source documentation. Instead, linkage to national health care registers allows the register to obtain data on all safety events of interest (regardless of suspected causal relationship to the treatments).

Another limitation of this study design is the absence of a control group which does not allow for comparative analysis of incidence rates with other treatments. This study will follow patients for a period of 3-years from therapy initiation, assuming continued participation and sufficient accrual of Ruxience patients is feasible. This period of follow-up may not be sufficient to adequately evaluate all safety events of interest, specifically malignancies. Conclusions may not be generalisable outside of the 3-year period since initiation of therapy.

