## **12. PLANS FOR DISSEMINATING AND COMMUNICATING STUDY RESULTS**

Annual summary reports will be generated. Analysis using linked register data through 3 years of follow up will be the basis for a final report. Data may be used in regulatory communications external to Sweden for contextualisation purposes. Manuscripts based on specific endpoints of interest may be developed for publication purposes.

In the event of any prohibition or restriction imposed (eg, clinical hold) by an applicable competent authority in any area of the world, or if the investigator is aware of any new information which might influence the evaluation of the benefits and risks of a Pfizer product, Pfizer should be informed immediately.

In addition, the investigator will inform Pfizer immediately of any urgent safety measures taken by the investigator to protect the study patients against any immediate hazard, and of any serious breaches of this NI study protocol that the investigator becomes aware of.

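### The milestone dates cannot deliver the 3 years of linked follow-up that the protocol states, and one common closing date does not give each patient 3 years from initiation

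*Protocol*

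**What the plan says.** The Abstract fixes the start of the study period: "The Study Start Date is defined as the date when the first patient diagnosed with RA in ARTIS initiates treatment with Ruxience". Section 9.3.2 fixes its end: "The Study End Date is defined as 3 years after the Study Start Date". This is one calendar date for everyone. Section 9.5 admits all eligible initiators during the study period, with no earlier close of entry.

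On data availability, the section 6 footnote reads "End of data collection is the planned date on which the analytical dataset will be first completely available", and the date given is 31 December 2023 (estimated). The final report is estimated for 31 December 2024, and another footnote requires it within 11 months of end of data collection. Section 9.4.2 gives "a lag time of between 1 and 2 years from when an event occurs until it can be analysed and reported" and attributes the delay to annual curation of the Patient and Cancer registers: "data from each year is only made available after internal processing, usually 9 to 12 months later". Processing of data requests comes on top.

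On follow-up, section 9.9 says "This study will follow patients for a period of 3-years from therapy initiation", subject to continued participation and sufficient accrual. Section 12 says "Analysis using linked register data through 3 years of follow up will be the basis for a final report".

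**The concern.** Three statements do not fit together: the date on which the dataset is complete, the stated register lag, and 3 years of linked follow-up. If the dataset closes on the planned date, the last part of the study period contributes no Patient or Cancer Register outcomes. The final report would then rest on less follow-up than section 12 says.

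The per-patient statement in section 9.9 is a separate conflict. A closing date anchored to the first patient gives 3 years only to patients who start on that day. This matters most for malignancy, where section 9.9 itself doubts that 3 years is long enough.

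A third, smaller conflict is the interval between end of data collection and the final report.

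A conditional risk to the rates follows from the first conflict. Section 9.3.2 censors at death, emigration and end of study follow-up and names no register-coverage date. If person-time ran on after event capture had stopped, the denominators would include time in which no event could be seen.

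**Working it through.** The plan's own figure is 3 years of follow-up. It cannot be reproduced from the plan's own dates.

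**Inputs.** Dataset complete 31 December 2023, and final report 31 December 2024 within 11 months (section 6). Release by calendar year, usually 9 to 12 months later, with a total lag of 1 to 2 years (section 9.4.2). Study End Date = first initiation + 3 years (section 9.3.2). EU approval 1 April 2020 (section 7). Entry throughout the period (section 9.5). The first-patient date is not given. I assume only that it does not precede EU approval.

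**1. Last linked date.** Data for 2022 are released about September to December 2023, and data for 2023 about September to December 2024. A dataset complete on 31 December 2023 therefore reaches 31 December 2022 at best. With the full 2-year lag it reaches 31 December 2021.

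**2. Earliest Study End Date.** 1 April 2020 + 3 years = 1 April 2023. The gap after 31 December 2022 is at least 3 months. Any later first patient widens it.

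**3. Longest linked follow-up.** 1 April 2020 to 31 December 2022 = 2.75 years. With a cut at 31 December 2021 it is 1.75 years. Three full years by 31 December 2022 would need a first initiation by 31 December 2019, before approval.

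**4. Follow-up per patient.** A patient who starts *t* years after the first patient has at most 3 − *t* years to the Study End Date. This equals 3 only at *t* = 0, before any register lag is counted.

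**5. Reporting interval.** 31 December 2023 + 11 months = 30 November 2024. The planned date is 31 December 2024, which is 12 months.

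**6. Conditional effect on rates.** Suppose person-time ran to the Study End Date (T = 3 years after the first patient) while events stopped at the last linked date (*c* years after the first patient). With a constant event rate and no dropout, estimated rate / true rate is

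- *c*/T if all patients start on day 0;
- (*c*/T)² if accrual is uniform, because person-time then grows with the square of elapsed time.

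With the cut at 31 December 2022:

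| Assumed first patient | *c* (years) | Understatement, day-0 start | Understatement, uniform accrual |
|---|---|---|---|
| 1 April 2020 | 2.75 | 1 − 2.75/3 = 8% | 1 − (2.75/3)² = 16% |
| 14 October 2020 | 2.21 | 1 − 2.21/3 = 26% | 1 − (2.21/3)² = 46% |
| 1 January 2021 | 2.00 | 1 − 2.00/3 = 33% | 1 − (2.00/3)² = 56% |

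If person-time stops at the last linked date, the ratio is 1 and there is no understatement. Steps 1 to 5 use no accrual assumption; step 6 does.

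**The case against.** The strongest reply concerns the rates. Nothing in the protocol runs person-time past register coverage, and section 9.7 leaves detailed methods to a statistical analysis plan that is not at hand. A data cut by register is the sort of detail such a plan commonly holds. This stands. A reader might infer that the reported rates will be biased low, or that every rate is affected, and the documents support neither. Section 9.4.2 ties the delay to curation of the Patient and Cancer registers and gives no release time for the Medical Birth Register, which supplies the pregnancy endpoint. For infections and cardiovascular events, the 270-day window after the last dose ends person-time in patients who stop. The figures in step 6 therefore apply mainly to malignancy and NMSC, and only if no cut-off is set.

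A reader might also infer a mean follow-up of 1.5 years, or that only a third of patients reach 2 years. Both need uniform accrual, which the protocol does not state; early uptake would give more follow-up.

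Section 12 does not mention therapy initiation, and its 3 years can be read as the study period. That is fair, but on that reading the linked data still fall at least 3 months short. The caveat in section 9.9 covers participation and accrual; it covers neither the common closing date nor the lag.

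It may also be said that the dates are estimates, that the release time is only the usual one, and that the lag is disclosed openly. All true, yet the disclosed lag is exactly what the milestone does not allow for. If 31 December 2023 was meant as the end of the event window, the footnote defining it is wrong. Moreover, 2023 data released between September and December 2024 would leave about 0 to 3 months for linkage, analysis and reporting.

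Finally, this is a voluntary, descriptive study without a comparator. That limits the consequences but does not reconcile the text.

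**Conclusion.** The point holds as a conflict between stated dates and stated follow-up. On the usual release times in section 9.4.2, and with no first patient before EU approval, at least the last 3 months of the study period lack linked Patient and Cancer Register outcomes. No patient can have more than 2.75 years of linked follow-up, against the 3 years in section 12. Independently of the lag, the 3 years from initiation in section 9.9 is available only to patients who start on the first day. The planned reporting interval exceeds its own limit by one month.

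Understatement of rates is a conditional risk and not an established defect. Its illustrative size is 8% to 33% with all patients starting on day 0, or 16% to 56% with uniform accrual. These ranges rest on assumed first-patient dates from 1 April 2020 to 1 January 2021, a constant event rate, no dropout and a cut at 31 December 2022.

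**What to change.** 1. Section 6: either move end of data collection to after release of the register year that contains the Study End Date, and set the final report within 11 months of it; or keep the dataset date, state that linked events run only to 31 December 2022, and align the report date with the 11-month limit. Under the first option, a Study End Date in 2023 implies data released about September to December 2024. A dataset complete on 31 December 2024 would then put the report at 30 November 2025 at the latest.
2. Section 9.9: state follow-up as up to 3 years, depending on the date of initiation. Section 12: name the linked period actually covered. Do not write in an assumed mean follow-up.
3. Section 9.3.2, as a safeguard: for each endpoint, end both events and person-time at the earlier of the Study End Date and the last complete date of the register supplying that endpoint. If the statistical analysis plan already does this, a cross-reference is enough.

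The cost is a few sentences and revised dates, plus either a later final report or a shorter stated follow-up.
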